Secondary Study Objectives	
 • To determine whether time to diagnosis (for ACS and no ACS) is significantly shortened and rates of direct discharge from the emergency department are increased in the interventional arm vs. standard of care • To determine a) the additional number of invasive coronary angiograms in both arms and b) to determine the number of coronary revascularization procedures. • To determine the safety of immediate ED discharge after a normal cardiac CT defined as the occurrence of ACS within 48-72 hours after discharge. • To determine whether subsequent testing and follow-up, including invasive coronary angiograms, diagnostic (imaging) tests, interventions, repeat ED visits for cardiac related problems and repeat hospitalizations for chest pain or equivalent during 28 days after hospital discharge is decreased in the interventional arm, compared to SOC. • To determine the two study arms in terms of rates of MACE within 28 days. • To compare the two study arms in terms of rates of MACE within one and two years. • To estimate and compare the sensitivity, specificity, NPV and PPV of contrast-enhanced CT and non-contrast CT, with clinical diagnosis of ACS as the reference standard. • To determine whether the cost of care (per TSI) for index hospitalization and after 28 days is decreased by implementing cardiac CT into the early ED evaluation of patients with acute chest pain. • To determine the cost-effectiveness of incorporating cardiac CT into

	the standard ED evaluation of patients with acute chest pain over a 28-day and lifetime horizon as compared to SOC.
Tertiary Study Objectives	
 • To determine whether CT leads to increased test burden after the initial tests during index hospitalization. • To compare the consistency of physician decisions management depending on the results of diagnostic testing (i.e. normal CT – what fraction is immediately discharged) • To determine whether hospital setting, availability of observation unit, CT experience of hospital and readers, and reader performance are associated with primary or secondary outcomes.
Primary Endpoint	The primary endpoint is time from ED presentation to hospital discharge. The length of hospital stay is defined as the time from ED presentation to the time of discharge note or order. This includes time in the ED, time in any institution-specific specialized chest pain unit, and time as an inpatient on the floor

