Duration of Study Participation	Participants will be followed during index ED visit/hospitalization. There will be a phone call at 48-72 hours for those discharged within 24 hours. All participants will receive a follow up phone call at 28 days post emergency room discharge.
Number of Subjects	1,000 subjects will be enrolled, with 500 each in the standard of care and interventional arms.
Number of Sites	9
Statistical Considerations	The primary aim of the study is to compare the two study arms in terms of a difference in mean length of hospital stay (LOS) between the two arms. We have conducted a power evaluation using the estimated mean and standard deviation based on observed data from ROMICAT I and simulated data based on health outcomes. We will have 95% power to detect a difference in 10 hours of LOS at a Type-1 error rate of 5% for an independent samples t-test using 500 patients in each arm.

Part I: Study Overview

The study is designed as a randomized, controlled, diagnostic, multicenter trial and will enroll 1,000 participants at nine sites over a 15 month period. Participants presenting with acute chest pain in the ED will be randomized to a standard of care arm (SOC) or interventional arm; patients in the interventional arm will receive standard evaluation supplemented by contrast-enhanced cardiac computed tomography (CT) imaging (Figure 1).

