In both arms, the initial Emergency Department (ED) evaluation (electrocardiogram [ECG], physical examination, clinical presentation, renal function lab, and medical history) will determine eligibility of patients. After randomization, standard of care will be performed in both arms. However, for patients randomized to the interventional arm, a CT will be performed. The following decisions made by the caregiver team will be tracked: admission or discharge after initial ED evaluation plus CT/other initial diagnostic test, in admitted participants, the length of hospital stay, the extent of further testing including serial cardiac markers and ECG, and other diagnostic tests or interventions. For safety reasons, participants discharged in less than 24 hours of ED arrival will receive a phone call 48-72 hours after discharge. All participants will receive a 28-day follow-up phone interview. The efficiency of each strategy will be determined by comparing 1) the length of hospital stay (primary endpoint), 2) the time to diagnosis (secondary endpoint), 3) the rates of ED discharge (secondary endpoint), 4) utilization of other diagnostic testing, i.e. invasive coronary angiograms, and resulting interventions, i.e. coronary revascularization procedures during index hospitalization and 28 days (secondary endpoint). The safety of the two strategies will be compared by determining the occurrence of adverse events within 48-72 hours in directly discharged patients as well as determination of major adverse cardiovascular events (MACE) within 28 days after discharge from the index hospitalization. We will also perform a cost and cost effectiveness analysis. In subsequent analyses, we will determine the patient, physician, and institutional factors that affect the primary endpoint or secondary endpoints.

Primary Objective:

To determine whether length of hospital stay is significantly shortened in the interventional arm vs. SOC.

Hypothesis:

Adding cardiac CT to the initial ED evaluation of subjects with acute chest pain decreases length of hospital stay.

Part II: Study Description

1. Background and Significance

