3.2 Secondary Aims

1. To determine whether time to diagnosis is significantly shortened and rates of direct discharge from ED are increased in the interventional arm vs. SOC.

A) Time to Diagnosis:

For **ACS**: Defined as the time from ED presentation until the first test during index hospitalization that leads to the diagnosis of ACS (tests may be biomarkers, CTA, ETT, nuclear imaging, stress ECHO or cardiac catheterization), For no ACS: Defined as the time from ED presentation defined as the final test during index hospitalization.

B) Admission to Hospital: Participants are considered to be admitted if the ED attending admitted the subject to a hospital floor (medical floor, step down unit, telemetry hospital floor, or intensive care unit)

Direct ED Discharge will include all subjects who are not included in (B).

Hypothesis: *ED evaluation of subjects with acute chest pain supplemented by cardiac CT significantly increases direct ED discharge rates and shortens time to diagnosis for both ACS positive and negative patients.*

2. To determine a) the additional number of invasive coronary angiograms, both arms, and b) to determine the number of coronary revascularization procedures.

Hypothesis: *ED evaluation of subjects with acute chest pain supplemented by cardiac CT will not increase the number of invasive coronary angiograms without revascularization or revascularizations during index hospitalization.*

3. To determine the safety of immediate ED discharge after a normal cardiac CT defined as the occurrence of ACS within 48-72 hours after discharge.

Hypothesis: *CTA has a high negative predictive value based on which immediate ED discharge should not compromise patient safety.*

4. To determine whether subsequent testing and follow up, including invasive coronary angiograms, diagnostic (imaging) tests, interventions, repeat ED visits for cardiac related problems, and repeat hospitalizations for chest pain or equivalent during 28 days after hospital discharge is decreased in the interventional arm compared to SOC,.

Hypothesis: *Incorporation of CTA in the evaluation of acute chest pain patients in the ED will not lead to decreased further testing to manage chest pain when as compared to the SOC arm.*

5. To compare the two study arms in terms of rates of MACE (major adverse cardiac events—cardiac death, AMI, revascularization, unstable angina, and rehospitalization) within 28 days.

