Follow-up phone call at 48-72 hours: Subjects who are discharged from the ED within 24 hours of presentation (for both randomization arms) will be contacted via telephone between 48 and 72 hours after discharge to avoid ascertainment bias. During this call, subjects will be interviewed to determine whether they have had any recurrent symptoms suggestive of myocardial ischemia and and/or whether they needed to seek further medical attention following their emergency department visit. If these phone attempts at 48 and 72 hours are not successful, a final attempt will be made at 96 hours to contact the subject

NOTE: If a subject is discharged on a Thursday, the 48-72 hour phone call may be extended to 96 hours. In the rare circumstance that a subject is discharged on a Thursday and the following Monday is a holiday, the follow-up call can be made during the next working business day.

5.3 28 Day Follow up

Follow up 28 day phone call: All subjects will be interviewed via a telephone call 28 days post ED discharge (+4 weeks) to determine the occurrence of MACE and healthcare utilization using a standardized questionnaire. All cases of recurrent chest pain, hospital admissions, and diagnostic testing will be verified by review of medical records.

A reminder letter will be sent or phone call will be made to participants, two weeks prior to the 28-day follow up phone call. If unable to contact the participant by phone, mortality will be assessed online using the SSDI website.

6. Data Collection

The following subject data will be collected during index ED visit/hospitalization and follow up phone interviews:

- Subject demographic information
- Medical history, including cardiac risk factors and medications
- Description of recent pain episodes
- Vitals signs, ECG, cardiac biomarker results
- Cardiac CT imaging and other cardiac-related diagnostic testing data
- Adverse events

7. Statistical Considerations

A total of 1000 participants will be enrolled in this study. Enrollment is planned to be completed in 15 months.

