Screening data from a survey of clinical sites as well as published data indicate that the standard rate of invasive coronary angiograms in the target population is approximately 10%. According to our study guidelines we assume that most but not all participants with significant stenosis in CT (10% of participants) undergo invasive coronary angiography (notably those who also have a positive stress test and those who have high grade proximal stenosis or LAD stenosis). In addition, we assume that a minority of participants with indeterminate stenosis (<5%) and positive stress testing undergo invasive coronary angiography. Because of the moderate specificities of standard diagnostic testing up to 40% of participants who undergo cardiac catheterization have no significant CAD.^{15,16} Because the diagnostic accuracy of cardiac CT for the detection of coronary stenosis is comparable or better than standard diagnostic testing, we believe that there will be no increase in the rates of invasive coronary angiograms. If we define a 5% difference as an “acceptable” difference in cardiac catheterization rates than we will have an 84% chance of showing that the CT arm is significantly less than 5% worse than the standard arm at a one sided $p=0.05$ significance level.

Another key measure of utilization is the number of coronary revascularization procedures: In ROMICAT I there were 18 revascularization procedures performed in 368 patients (5%). Thus, we expect 5% procedures in the standard evaluation. If we assume that not all participants with significant stenosis will undergo coronary revascularization (because if no MI it can be medically managed) and that cardiac CT may also avoid some angiograms by excluding disease, than we can realistically assume that there is not a difference between the two study arms. If we consider this in terms of a non-inferiority trial as above, we will have 80% power to rule a difference of 3.5%.

To compare the two study arms in terms of cardiac health care utilization within one year after index hospitalization. Health care utilization components will include invasive coronary angiograms, cardiac related diagnostic and lab testing, and ED visits.

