This analysis will be performed from the intent to treat perspective. CP and CT related health care utilization will be assessed using medical record review. Measures of key components of utilization will be compared across the two study groups using procedures appropriate for each measure (rate or count).

We expect that the rate of additional cardiac work-up will be 29% in the SOC arm and will be 14% in the interventional arm. We will have >95% power to detect this difference.

We expect that the rate of hospital admissions with additional diagnostic cardiac testing will be 9.3% in the SOC arm and will be 4% in the interventional arm. We will have >95% power to detect this difference.

We expect that the rates of these measures will be associated with the CT findings at index hospitalization.

To evaluate the cost and cost-effectiveness of incorporating cardiac CT into the standard ED evaluation of patients with acute chest pain

These analyses will be performed by the Decision Analysis and Cost-Effectiveness Center (DACE). Therefore, the sites will collect and provide the necessary data to the DACE and the costs will be derived from the cost-accounting database (TSI). As a first step, incorporating cardiac CT into the standard evaluation of patients with acute chest pain will be tested for cost-saving over a 28-day and lifetime span as compared to standard care. Further on, cost-effectiveness of incorporating cardiac CT into the standard ED evaluation of patients with acute chest pain will be determined using first-order Monte Carlo microsimulations.

To compare the two study arms in terms of rates of MACE (cardiac death, AMI, revascularization, unstable angina, and rehospitalization) within 28 days.

The analysis for this secondary aim will be performed from the intent to treat perspective. The occurrence of MACE will be assessed via patient follow-up and medical chart review. The primary analysis for this aim will be performed at the patient level by determining whether any MACE occurred or not. Event rates will be estimated and compared between study groups using exact procedures. In a secondary analysis, the rates of each type of MACE will be examined separately.

Sample Size- Safety Considerations- Missed ACS: Mistaken discharges are the primary safety issue in this study. All available data indicate that the absence of any detectable CAD (absence

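### Section 7.2 plans and powers a one-year utilisation comparison, but the protocol schedules no data collection beyond the 28-day call and gives no rates or power for the 28-day aim

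*Protocol*

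**What the plan says.** **The one-year text.** Protocol Section 7.2 lists, as a secondary analysis, "To compare the two study arms in terms of cardiac health care utilization within one year after index hospitalization". It covers invasive angiograms, cardiac diagnostic and laboratory testing, and ED visits, by intention to treat, with medical record review as the data source. Two power statements follow:

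- Additional cardiac work-up: 29% under standard of care, 14% under CT, power above 95%.
- "We expect that the rate of hospital admissions with additional diagnostic cardiac testing will be 9.3% in the SOC arm", against 4% under CT, power again above 95%.

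**The 28-day text.**

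- Synopsis, duration of participation: "All participants will receive a follow up phone call at 28 days post emergency room discharge".
- Part I overview: diagnostic testing and resulting interventions are compared "during index hospitalization and 28 days (secondary endpoint").
- Section 3.2, Aim 4: subsequent testing, interventions, repeat ED visits and repeat hospitalisations over the 28 days after discharge.
- Section 5.3: "All subjects will be interviewed via a telephone call 28 days post ED discharge (+4 weeks"), covering MACE and health care use, with reported events verified from records.
- Section 6: "The following subject data will be collected during index ED visit/hospitalization and follow up phone interviews".

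**A further leftover.** The synopsis still lists the objective "To compare the two study arms in terms of rates of MACE within one and two years". Section 3.2 has no such aim, and Section 7.2 has no such analysis.

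**Direction.** Aim 4 asks whether subsequent testing is reduced under CT. The hypothesis printed beneath it says CT "will not lead to decreased further testing to manage chest pain". The synopsis hypothesis says further testing will not rise. Section 7.2 powers a reduction of about half.

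**The concern.** The horizon that is analysed and powered is not the horizon at which data are to be collected. Section 7.2 powers a one-year comparison that Section 3.2 does not list and Sections 5 and 6 do not supply. Aim 4 is listed and has a data source, but Section 7.2 gives it no rates and no power.

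Two things are at stake. First, a reader may credit the 28-day utilisation aim with more than 95% power when the figures were stated for one year, a period about 13 times as long (365/28 = 13.0). Second, with two horizons in the text and an aim and hypothesis that point different ways, the horizon and the direction of the test could be settled after the data are seen.

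**Working it through.** **Inputs.** 500 per arm (synopsis, number of subjects). Rates of 29% against 14% and 9.3% against 4% (Section 7.2). Alpha and sidedness are not stated for this comparison. I assume 0.05, the level used for the discharge-rate comparison in the same section, and compute both sidednesses.

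**Formula.** Normal approximation with pooled variance under the null: power = Φ[(d − z·SE0)/SE1], where d = p1 − p2, SE0 = √(2·p̄(1 − p̄)/n), SE1 = √((p1(1 − p1) + p2(1 − p2))/n), and z = 1.960 (two-sided) or 1.645 (one-sided).

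**1. Reproducing the plan's figures at its own rates.**

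*Work-up, 29% against 14%.* d = 0.150, p̄ = 0.215, SE0 = 0.02598, SE1 = 0.02555. Two-sided: (0.150 − 0.0509)/0.02555 = 3.88, power above 99.9%. The claim reproduces.

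*Admissions with testing, 9.3% against 4%.* d = 0.053, p̄ = 0.0665, SE0 = 0.01576, SE1 = 0.01567.

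- Two-sided: (0.053 − 0.03089)/0.01567 = 1.41, power 92.1%.
- One-sided: (0.053 − 0.02592)/0.01567 = 1.73, power 95.8%.

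| Method, 9.3% against 4% | Two-sided 0.05 | One-sided 0.05 |
|---|---|---|
| Pooled z | 92.1% | 95.8% |
| Unpooled z | 92.3% | 95.9% |
| Arcsine | 93.0% | 96.3% |
| Continuity-corrected | 90.0% | 94.5% |
| Exact enumeration, chi-square | 92.8% | not run |
| Exact enumeration, Fisher | 91.0% | not run |

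No two-sided method reaches 95%; that would need 572 per arm (pooled z). The stated figure is recovered only one-sided and without continuity correction.

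**2. Comparing the horizons.** The last contact falls at 28 days, or at most 28 + 28 = 56 days with the window. Sections 5 and 6 describe no collection after that. The only current text that sets a longer horizon is the one-year heading in Section 7.2 and the MACE line in the synopsis.

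**3. Do the powers carry over to 28 days?** The protocol gives no 28-day rates, so this step is illustrative. Let f be the share of the year's risk that falls in the first 28 days. I use two models: a proportional share of events (rate = p·f) and a share of cumulative hazard (rate = 1 − (1 − p)^f). Two-sided 0.05, 500 per arm:

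| f | Work-up: share of events / of hazard | Admissions: share of events / of hazard |
|---|---|---|
| 28/365 (even accrual) | 30% / 39% | 15% / 15% |
| 0.25 | 75% / 85% | 37% / 40% |
| 0.50 | 97% / 99% | 65% / 67% |

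Worked example, even accrual by share of events: 0.29 × 28/365 = 2.2% and 0.14 × 28/365 = 1.1%, giving 30%.

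The range is wide and the choice of model alone moves it by up to 10 points. What it shows is that 28-day power cannot be read from the protocol. For admissions, no f up to 1 gives 95% two-sided, since f = 1 gives 92.1%.

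**The case against.** **Record review could supply one-year data.** Section 7.2 names medical record review, not the telephone call, as the source for this analysis. A reader might infer from the missing one-year contact that the analysis cannot be run, or that no data will exist. The documents do not support that: a later chart review is conceivable. What stands is that none is scheduled, and that after the 28-day call nothing is planned that would bring care at other hospitals to light.

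**The listed aim does have data.** A reader might also infer that a listed secondary aim lacks a data source. It does not. Aim 4 is a 28-day aim, and Section 5.3 provides for it. The fault lies in the Section 7.2 paragraph.

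**The 9.3% against 4% figure may not be a miscalculation.** The angiogram analysis shortly before it is one-sided at 0.05, and at that level 95.8% agrees with the claim. But that test is for non-inferiority and this comparison is for a reduction, so one-sidedness cannot be taken over without a statement. The supportable point is unstated sidedness, with the claim failing if the test is two-sided.

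**The 28-day powers are hypothetical.** This is correct. They should not be read as showing that the 28-day comparison is underpowered; they show only that its power is unknown.

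**The direction conflict may be a slip.** The hypothesis under Aim 4 may have been meant to say increased, as the synopsis does, and the aim itself agrees with the powered reduction. It is a lesser wording item, but as printed the statements do not agree.

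**Conclusion.** The point holds in this form. The one-year utilisation analysis is unsupported as designed, because the current protocol plans no collection beyond the 28-day call. The two power statements belong to the one-year horizon and do not carry over to the 28-day comparison, for which no rates or power are given. That conflict lies wholly within current text and needs no assumption.

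On the plan's own rates, the work-up claim is correct (above 99.9%). The admissions claim is about 92% two-sided and 95.8% one-sided at 0.05. This assumes 500 evaluable participants per arm and alpha 0.05.

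This should be fixed, but it is not critical. It concerns one of eight secondary aims. The sample size is justified on length of stay, and neither the primary analysis nor the 28-day MACE analysis is affected.

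**What to change.** 1. In Section 7.2, change the horizon of this comparison from one year to 28 days, to match Aim 4 and Section 5.3. If the sponsor does want one year, a scheduled data source has to be added instead.
2. Delete the one- and two-year MACE objective from the synopsis.
3. Remove the two power sentences, or replace them with 28-day rates that the sponsor can justify, a stated sidedness and recomputed power. The accrual scenarios above are not a basis for those rates.
4. If 9.3% against 4% is kept anywhere, state 92% (two-sided) or 96% (one-sided 0.05).
5. As a lesser item, reword Aim 4, its hypothesis, the synopsis hypothesis and the powered difference so that they share one direction.

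The cost is protocol wording, plus the work of justifying 28-day rates if a power statement is retained. Aligning to 28 days changes no participant procedure. The stated power for this aim may become less favourable.

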To develop a preliminary decision-analytic Markov model to predict the long-term consequences of four competing strategies 47 in the ED evaluation of subjects with acute chest pain.

Methods: The model consists of the six health states: chest pain, healthy, early heart disease, undiagnosed CAD, diagnosed CAD and death. Subjects start in the chest pain state. The probability that the chest pain is caused by CAD depends on the underlying risk of CAD as

determined by age, gender, and cardiovascular risk factors. As simulated subjects progress through the model, CAD (if present) can remain stable or progress. Subjects may die from cardiovascular disease or other causes, at rates determined by disease stage and demographics. By simulating hypothetical cohorts of subjects, we determined quality-adjusted life expectancy (QALE), quality-adjusted life year (QALY), and cost-effectiveness ratios for competing strategies.

We considered four competing strategies for subjects presenting with chest pain to the ED:

1) *admission*, in which all subjects are admitted to the hospital for further evaluation; 2) *discharge*, in which all subjects are discharged directly home from the ED; 3) *cardiac CT with conservative treatment*, in which all subjects without any evidence of CAD are discharged and all other patients are admitted and undergo stress testing; and 4) *cardiac CT with aggressive treatment*, which is similar to strategy 3 but sends subjects with evidence of significant stenosis directly for invasive coronary angiography. It is important to note that the model permits an evaluation of each strategy using a similar cohort of subjects. The model also permits an evaluation of estimate life expectancy and lifetime costs.

Results

Strategies involving cardiac CT were associated with lower ED costs and incremental improvements in QALE when compared to a strategy of admission for all subjects. Relative to admitting all subjects, the use of cardiac CT yielded savings in ED and hospital costs ranging from \$1,800-\$2,200 in men and women ages 30-40, and from \$500-\$1,200 men and women ages 60-70 respectively. The incremental cost-effectiveness of strategies involving cardiac CT, compared with a strategy of discharging all subjects, ranged from \$94,100-\$267,200 per QALY in men and \$74,800-\$326,100 per QALY in women.

Conclusions

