This preliminary decision model suggests that strategies involving cardiac CT are associated with lower ED costs and incremental improvements in QALE in both men and women across all ages. The precision of the model will be greatly enhanced by input of real clinical scenarios derived from this proposal.

3. Study Objective/Specific Aims

This primary objective of this protocol is to assess the efficiency of implementing cardiac CT into the diagnostic workup of patients with acute chest pain, normal initial biomarkers, and normal or non-diagnostic ECGs. Study participants will be patients with acute chest pain and low to intermediate likelihood of ACS and will be randomly assigned to the SOC arm or the interventional arm; patients in the interventional arm will receive the standard of care supplemented by cardiac CT.

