28 Days: Defined as 28 days post the day of discharge from index hospitalization.

Hypothesis: *The rates of MACE in both arms during the 28 day follow up period will be similar.*

6. To estimate and compare the sensitivity, specificity, NPV and PPV of contrast-enhanced CT and non-contrast CT, with clinical diagnosis of ACS as the reference standard.

Hypothesis: *The test characteristics of contrast enhanced CT will be significantly better than those of a non-contrast CT for the diagnosis of ACS.*

7. Determine whether cost of care (per TSI) for index hospitalization and after 28 days is decreased by implementing cardiac CT into the early ED evaluation of patients with acute chest pain.

Hypothesis: *Incorporation of cardiac CT into standard ED evaluation of patients with acute chest pain will decrease the cost of care.*

8. Determine the cost-effectiveness of incorporating cardiac CT into the standard ED evaluation of patients with acute chest pain over a 28-day and lifetime horizon as compared to SOC.

Hypothesis: *Incorporating cardiac CT into the standard evaluation of patients with acute chest pain will be cost-saving and cost-effective over a 28-day and lifetime horizon.*

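### Section 7.2 lets first-order microsimulation determine cost-effectiveness, which leaves out the sampling error of inputs estimated from about 500 patients per arm

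*Protocol*

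**What the plan says.** Aim 8 (Protocol section 3.2) carries a directional hypothesis: cardiac CT "will be cost-saving and cost-effective over a 28-day and lifetime horizon". Section 7.2 gives the analysis in two steps, assigned to a dedicated decision-analysis centre, with costs taken from the sites' cost-accounting database.

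- First step: CT "will be tested for cost-saving over a 28-day and lifetime span as compared to standard care". The test is not named.
- Second step: cost-effectiveness "will be determined using first-order Monte Carlo microsimulations". Section 7.2 names no other method for this conclusion.

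The trial is meant to feed the model. Of the preliminary decision model, section 2.1.3 says: "The precision of the model will be greatly enhanced by input of real clinical scenarios derived from this proposal". On the trial's size, the Study Synopsis says: "1,000 subjects will be enrolled, with 500 each in the standard of care and interventional arms". The last planned contact is the 28-day call (section 5.3).

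The protocol gives no number of simulated patients, no alpha for the cost aims and no decision rule for cost-effectiveness. It does not mention a second-order (probabilistic) analysis.

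**The concern.** A model result of this kind has two sources of error. One is the random path of each simulated patient given the inputs (first-order). The other is uncertainty about the inputs themselves, here costs, discharge rates and event rates estimated from a finite trial (second-order). First-order microsimulation represents only the first. That part can be made as small as one likes by simulating more patients, and this adds no knowledge about the population. The second part is fixed by the trial's 500 patients per arm and does not appear in the output.

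Section 7.2 therefore ties a directional hypothesis to a method whose only error measure is unrelated to the amount of trial data. The lifetime part of the cost-saving test is exposed in the same way. Follow-up stops at 28 days, so lifetime costs have to be modelled, and the first-order model is the only one that section 7.2 names. At stake is whether a reader of the economic results can tell a real saving from chance in the inputs.

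**Working it through.** The protocol states no figure for this analysis, so there is nothing of its own to reproduce. The check asks how far first-order error understates total error.

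**Inputs**
- n = 500 patients per arm (Study Synopsis).
- M = number of simulated patients per arm. The protocol gives none, so a range is shown.
- SD = patient-level standard deviation of cost. The protocol gives none. It cancels in steps 1 to 3.
- Assumption: the modelled cost difference is driven wholly by trial-estimated arm inputs with that patient-level SD, and there is no true difference.

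**Step 1. Variances of the modelled difference**
- From trial-estimated inputs: 2·SD²/n
- From first-order noise: 2·SD²/M
- Total: 2·SD²·(1/n + 1/M)

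**Step 2. False-positive rate if only first-order error is used**

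The difference is divided by SD·√(2/M), but its true standard error is SD·√(2/n + 2/M). The ratio of true to assumed standard error is √(1 + M/n). The two-sided 5% test then rejects with probability

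2·[1 − Φ(1.96/√(1 + M/500))]

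| M per arm | 1.96/√(1 + M/500) | False-positive rate |
|---|---|---|
| 500 | 1.386 | 16.6% |
| 1,000 | 1.132 | 25.8% |
| 5,000 | 0.591 | 55.5% |
| 10,000 | 0.428 | 66.9% |
| 100,000 | 0.138 | 89.0% |
| 1,000,000 | 0.044 | 96.5% |

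A simulation of 20,000 trials per setting, with log-normal costs, gave 26.1%, 66.3% and 96.5% for M = 1,000, 10,000 and 1,000,000.

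**Step 3. With input uncertainty carried through**

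Dividing by SD·√(2/500 + 2/M) gives 5.0% for every M. A direct test on 500 against 500 observed costs rejected in 5.0% to 5.2% of the simulated trials.

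**Step 4. How much uncertainty is left out**

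The 95% half-width from the trial inputs, relative to mean cost, is 1.96·√(2/500)·(SD/mean) = 0.124·(SD/mean). If cost varies as length of stay does in section 7.1 (43.2/40.5 = 1.07, an assumption), this is about 13%. For SD/mean from 0.5 to 1.5 it runs from about 6% to 19%.

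**The case against.** The strongest reply is that the protocol describes no significance test on simulated patients. It gives no alpha and no number of simulated patients. Aims 1 and 6 speak of significance in their hypotheses, and Aim 8 does not. The preliminary model in section 2.1.3 reported "quality-adjusted life expectancy (QALE), quality-adjusted life year (QALY), and cost-effectiveness ratios for competing strategies", without p-values. This stands. A reader might infer from the table that the trial would declare a false cost difference in 67% to 96.5% of cases. The protocol does not support that, because those rates need 10,000 to 1,000,000 simulated patients per arm and a test that nobody has specified. With 500 to 5,000 the same arithmetic gives 17% to 55%.

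A reader might also infer that all the cost claims rest on Monte Carlo error. They do not. The cost-saving comparison is a separate first step, and Aim 7 covers cost of care for the index stay and after 28 days. On observed patient-level costs an ordinary test keeps its 5%. Nor is it a defect of first-order simulation that, with no true difference, the point estimate favours CT half the time. That is so of any point estimate.

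Two further replies stand in part. The model in section 2.1.3 has six health states, with death rates set by disease stage and demographics, so some inputs may come from outside the trial and the table would change. And the handling of parameter uncertainty may sit in an analysis or economic plan that is not shown, so its absence alone is no error. But section 7.2 does more than stay silent: it names a first-order run as what determines the conclusion. That sentence would need correcting even if a fuller plan exists.

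**Conclusion.** The point holds as a poor choice of stated method for a secondary aim. First-order microsimulation, as named in section 7.2, cannot express the uncertainty that 500 patients per arm leave in the cost-effectiveness result, or in the lifetime part of the cost-saving test if the same model serves it. Any interval or p-value drawn from it would depend on how many patients were simulated.

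The false-positive rates are an illustration under three assumptions: the chosen M, a test against first-order error alone, and a difference driven wholly by trial inputs. Under these, every M shown lies well above 5%. The left-out uncertainty of about 13% of mean cost (6% to 19%) rests on the assumed spread of costs. The 28-day cost comparison is outside the point, provided it is done on observed costs from the cost-accounting database.

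**What to change.** Amend the cost-effectiveness paragraph of section 7.2 as follows.

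- Run the microsimulation inside a second-order (probabilistic) loop. In each pass, draw the trial-derived inputs from their sampling distributions, or re-estimate them after bootstrapping patients within arm.
- Report an interval for incremental cost and for net benefit, and the probability of being cost-effective.
- State that no p-value or interval will be based on the number of simulated patients. Use that number only to make Monte Carlo noise negligible.
- Apply the same rule to the lifetime part of the cost-saving test, and say that the 28-day part is tested on observed patient-level costs.

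This needs no new data and keeps the same model. The cost is a change of wording and more computing time for the modelling group. The intervals will be wider, and the economic conclusion may be less favourable to CT than a first-order run would suggest.
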